## LIST OF ABBREVIATIONS

AE	Adverse Event
ANCOVA	Analysis of Covariance
CFR	Code of Federal Regulations
CIOMS	Council for International Organizations of Medical Science
CRF	Case Report Form
FDA	Food and Drug Administration
FDAAA	Food and Drug Administration Amendments Act of 2007
GCP	Good Clinical Practice
ICH	International Conference on Harmonisation
ICH E6	International Conference on Harmonisation Guidance for Industry, Good Clinical Practice: Consolidated Guidance
ICMJE	International Committee of Medical Journal Editors
IDE	Investigational Device Exemption
IRB	Investigational Review Board
ISO 14155:2011	International Organization for Standardization Good Clinical Practices for Clinical Investigations of Medical Devices
LED	Light emitting diode
LSMEANS	Least-squares Means
MedDRA	Medical Dictionary for Regulatory Activities
PI	Principal Investigator
QC	Quality Control
SAE	Serious Adverse Event
SAP	Statistical Analysis Plan
SMC	Safety Monitoring Committee
SOC	System Organ Class
UP	Unanticipated Problem
VAS	Visual Analog Scale

## PROTOCOL SUMMARY

TITLE	Feasibility Study of a 950 nm Wavelength LED Device for Non-invasive Lipolysis of the Flanks
SUMMARY	Open-label, feasibility study comparing the tissue temperature profile of a 950 nm LED device and a 1060 nm diode laser for non-invasive lipolysis of the flanks. The study will enroll up to 10 subjects requesting non-invasive lipolysis of the flanks. Each subjects will receive a single treatment with each device on opposite flanks. Tissue temperatures in the treated areas will be recorded and compared.
OBJECTIVES	The objective of this clinical study is to compare the tissue temperature profiles of the LED device and diode laser device and to compare safety in the treatment of lipolysis of the flanks.
ENDPOINT	Primary objective 

• Temperature profile comparison at various tissue depths.

 Safety 

• Subject's assessment of discomfort and pain as measured by a 10 cm visual analog scale (VAS).

• Subjects experiencing a treatment-related adverse event (AE).

POPULATION	The study will enroll up to 10 male and female subjects, ≥ 18 years of age who are seeking non-invasive lipolysis of the flanks.
PHASE	Feasibility
NUMBER OF SITES	one
DESCRIPTION OF DEVICE	The investigational device uses LED technology. The 1060 nm diode laser has been approved by the FDA for non-invasive lipolysis of the flanks.
STUDY DURATION	Two months
PARTICIPANT DURATION	One day plus a telephone follow-up after one week

## 2 INTRODUCTION: BACKGROUND INFORMATION AND SCIENTIFIC RATIONALE

### 2.1 BACKGROUND INFORMATION

Non-invasive body contouring is gaining popularity in the United States and the field is advancing at a fast pace with the vast majority of cases using non-invasive methods. Various technologies exist today including cryolipolysis, radiofrequency, ultrasound, injection lipolysis and laser. When advancing to a non-invasive approach to lipolysis, an external device is required. In 2015, the FDA approved a 1060 nm diode laser for fat reduction (Cynosure SculpSure). The laser leads to injury of the adipocytes through direct heating of the tissue. Energy creates movement within the molecules of the exposed tissue, which then generates heat. A controlled temperature of 42-47 °C must be maintained at the site of adipocytes. At this temperature, the cell membranes of the adipocytes lose their structural integrity leading to cell death. Upon cell injury and death, the body naturally eliminates the contents of the adipocytes. The laser targets unwanted adipocytes while leaving the overlying skin and adnexal structures unharmed. In addition, melanin is minimally targeted so the device can be used in all skin types.

### 2.2 RATIONALE

A new emerging technology in the area of aesthetic medicals device is LED (light-emitting diode) photo-modulation. It is currently being used to stimulate fibroblasts to produce collagen and to destroy bacteria on the skin. In this study, a 950 nm LED investigational device is being evaluated to determine if it is able to target adipocytes by maintaining a controlled temperature of 42-47 °C, similar to the reference device. In addition, the safety of the LED device will be compared to the reference device.

The use of this LED device has been determined to present non-significant risk for the intended use in this study, because the device is not:

- Intended as an implant and presents a potential for serious risk to the health, safety, or welfare of a subject;
- Is purported or represented to be for use supporting or sustaining human life and presents a potential for serious risk to the health, safety, or welfare of a subject;
- Is for a use of substantial importance in diagnosing, curing, mitigating, or treating disease, or otherwise preventing impairment of human health and presents a potential for serious risk to the health, safety, or welfare of a subject; or
- Otherwise presents a potential for serious risk to the health, safety, or welfare of a subject.

This study will be conducted in compliance with the protocol and according to Good Clinical Practice standards.

## 2.3 POTENTIAL RISKS AND BENEFITS

### 2.3.1 KNOWN POTENTIAL RISKS

The potential risks for adverse effects of the treatment procedure include but are not limited to blistering, burns, excessive edema or erythema, infection, scarring and post-inflammatory hyperpigmentation.

### 2.3.2 KNOWN POTENTIAL BENEFITS

If the subject agrees to participate in this study, he/she will be contributing to the understanding of the safety and efficacy of the device. This understanding may lead to optimization of the treatment with this device. In addition the subject may benefit from reduction in unwanted adipocytes.

## 3 OBJECTIVES AND PURPOSE

The study is being conducted to evaluate the feasibility and safety of a LED device for non-invasive treatment of the flanks.

### Primary objectives

Tissue temperature profile of the LED device compared to the diode laser device.

### Safety

Subject's assessment of discomfort and pain as measured by a 10 cm visual analog scale (VAS).

Subjects experiencing a treatment-related adverse event (AE).

## 4 STUDY DESIGN AND ENDPOINTS

### 4.1 DESCRIPTION OF THE STUDY DESIGN

This is an open-label, comparative, single-center study to evaluate the feasibility and safety of a LED device and a diode laser device for non-invasive lipolysis of the flanks.

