#### 4.2.2 SECONDARY ENDPOINTS

### Safety objectives

Subject's assessment of discomfort and pain as measured by a 10 cm visual analog scale (VAS).

Subjects experiencing a treatment-related adverse event (AE).

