#### **Pre-Treatment**

Subjects will be instructed to avoid sun exposure of the target treatment areas for at least six weeks before treatment and to use broad spectrum sunscreen of no less than 30 SPF daily, replenishing it as often as needed throughout the course of the study and for six weeks after the treatment. In addition, tanning is to be strictly avoided. Subjects should not receive any treatment with a laser or other devices in the study treatment area throughout the course of this study and follow-up examinations.

Protective eye goggles will be worn by both the patient and site staff performing the treatment for the duration of the treatment session.

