#### **Treatment**

Based on the mild nature of treatment, anesthesia is not required. Treatment procedure should include positioning of the patient in a manner that enables access to the target treatment anatomical site. A water-based spray should be applied to the treatment area immediately prior to treatment.

Each subject will receive two consecutive treatments in the following order: the left flank of the abdomen will be treated with the diode laser device and the right flank of the abdomen will be treated with the LED device. The exact placement on the flank will be left to the principal investigator's judgement based on his assessment of individual subject requirements for treatment. Subjects will be treated on the same bilateral location with each device to ensure consistency of measurements. Both laser and LED applicators will be set to same output power level. Two levels will be used 41W (1.17W/cm^2) and 29W (0.83W/cm^2). The first level of 41W corresponds to initial heating for 4 minutes and the second level corresponds to duty cycle of 25 sec on and 10 sec off time. Total treatment time with each device will be 24 minutes (first 4 min at full power and next 16 min at duty cycle 25/10). Both device applicators have same output window dimensions and area 7x5 cm (35 cm^2). Both applicators are cooled by water chiller and therefore provided the same surface cooling temperature on skin.

Immediately (within 2 minutes) after treatment, 3 sterile thermocouple needles of different lengths (7-15 mm), will be inserted into the center of each applicator footprint. Temperature readings from each thermocouple needle will be recorded.

During treatment, subject reaction must be monitored and if the subjects verbally report an intolerable level of pain, treatment shall be ceased immediately.

The normal response to these treatments is transient erythema and edema. If any side effects occur other than a normal transient response, as indicated in the protocol, they will be recorded.

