## **Assessment**

The assessment of discomfort/pain based on the subject's report will be documented immediately (within 5 minutes) after treatment and before any subsequent treatment using the 10 cm VAS.

The investigator will examine the treated area and report immediate and short term response (30 minutes post-treatment) (pain during treatment, hemorrhage, burn, erythema, edema, purpura) using a 5 point scale: 1=none; 2=trace; 3=moderate; 4=marked; 5=severe.

The normal response to these treatments is transient erythema and edema. If any other side effects occur, as indicated in the protocol, they must be recorded. Subjects will be discharged from the clinic.

---

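### Nothing keeps subjects from knowing which device they are rating for pain, so expectation of unknown size and direction can enter the between-device VAS contrast, on top of the fixed side and order.

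*Combined protocol and SAP*

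**What the plan says.** - **Masking.** Section 4.1 states: "This is an open-label, comparative, single-center study to evaluate the feasibility and safety of a LED device and a diode laser device". The Protocol Summary and section 10.3 also call the study open-label. Section 10.1 mentions unblinding, but no masking procedure stands behind the word.
- **Aim.** Section 2.2 states: "In addition, the safety of the LED device will be compared to the reference device". The Protocol Summary gives the same aim among the objectives.
- **Outcome.** Section 4.2.2 lists, as one of two safety endpoints, "Subject's assessment of discomfort and pain as measured by a 10 cm visual analog scale (VAS". Under Assessment in section 7.3.2, the rating "will be documented immediately (within 5 minutes) after treatment and before any subsequent treatment using the 10 cm VAS", so each subject gives one score per device.
- **Assignment.** Section 7.3.2 (Treatment) gives every subject the diode laser on the left flank, then the LED on the right.
- **Features that bear on masking.** Section 7.3.1 says "Protective eye goggles will be worn by both the patient and site staff", without saying whether the eyewear blocks vision. Section 7.3.2 says "Both device applicators have same output window dimensions and area 7x5 cm", and also matches the output power level and water cooling. Section 6.1.2 describes the LED device as a console with an applicator belt. The laser's appearance and handling are not described.
- **Consent.** Section 13.3.1 requires the consent form to describe the study agent and procedures in detail.
- **Analysis.** Section 10.3 says the VAS will be analysed but names no contrast, interval or test. Section 10.4 gives no sample size calculation and a maximum of 10 subjects.

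**The concern.** A VAS score is the subject's own judgement. A subject who knows that one flank gets an approved laser and the other an investigational LED may rate them differently with no difference in sensation. Any part of that shift which subjects share passes into the mean within-subject difference, and a larger sample does not remove it. The study intends to compare safety between the devices, and pain is one of its two named safety measures. A between-device statement about pain would then mix the devices with what subjects expected of them. Nothing in the plan requires the subject to know which device is on which flank before scoring.

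**Working it through.** **No figure to reproduce.** The documents give no VAS standard deviation, margin, alpha or power. What follows is an illustration on assumed values.

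**Inputs.** n = 10 pairs (section 10.4, maximum). Assumed: SD of within-subject VAS differences 1.5, 2.0 or 2.5 cm; no true device difference; an expectation shift of 0.5 or 1.0 cm in the same direction for all subjects.

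**Step 1. Standard error.** SE = SD/√10:
- 1.5/3.162 = 0.47 cm
- 2.0/3.162 = 0.63 cm
- 2.5/3.162 = 0.79 cm

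With t(0.975, 9 df) = 2.262, the 95% half-widths are 1.07, 1.43 and 1.79 cm.

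**Step 2. Effect of a common shift.** The noncentrality is shift/SE. The chance that a two-sided 95% paired interval excludes zero comes from the noncentral t with 9 df. The chance that the mean has the expected sign is Φ(shift/SE).

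| SD (cm) | Shift (cm) | Shift/SE | Interval excludes zero | Mean in expected direction |
|---|---|---|---|---|
| 1.5 | 0.5 | 1.05 | 0.157 | 0.85 |
| 2.0 | 0.5 | 0.79 | 0.109 | 0.79 |
| 2.5 | 0.5 | 0.63 | 0.088 | 0.74 |
| 1.5 | 1.0 | 2.11 | 0.469 | 0.98 |
| 2.0 | 1.0 | 1.58 | 0.293 | 0.94 |
| 2.5 | 1.0 | 1.26 | 0.205 | 0.90 |

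With no shift the second-to-last column would be 0.05 and the last 0.50.

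**Step 3. How far this depends on a common direction.** If a fraction p of subjects shifts by +1 cm and the rest by −1 cm, the mean shift is (2p − 1) × 1 cm: 1.0 cm at p = 1, 0.5 cm at p = 0.75, and 0 at p = 0.5. Opposed expectations partly cancel and add variance instead. The documents do not indicate p.

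**Step 4. What masking leaves behind.** Suppose masking removes expectation entirely, but a side or order effect of 0.5 or 1.0 cm remains (SD 2 cm; 200,000 simulated studies of 10 subjects).

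| Side/order effect (cm) | Assignment | Mean bias (cm) | Test rejects |
|---|---|---|---|
| 0.5 | fixed, as planned | 0.50 | 0.109 |
| 0.5 | balanced 5/5 | 0.00 | 0.043 |
| 1.0 | fixed, as planned | 1.00 | 0.295 |
| 1.0 | balanced 5/5 | 0.00 | 0.031 |

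Masking without balanced assignment leaves the whole side or order effect in the device contrast. Rejection falls below 0.05 under balance because the effect then widens the spread of the differences without moving their mean.

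**Step 5. A guess question.** Asking subjects afterwards which side had the LED is uninformative under the present schedule. The right answer is always right flank, second, so a shared habit of calling the second device the new one looks like failed masking. Even with balance it is imprecise: 5 of 10 correct has an exact 95% interval of about 19% to 81%.

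**The case against.** The strongest reply is proportionality. This is a small feasibility study that says openly it is open-label. Pain is a secondary endpoint with no planned test, so the error rates above belong to an interval nobody proposes. The size and direction of any expectation effect are assumed: some subjects may fear a laser and others an unapproved device. All of this stands. It limits the weight of the point but does not remove it, because a descriptive difference in mean VAS carries the same bias as a tested one.

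A second reply is that masking would not rescue the comparison, because side and order are fixed for everyone, and a subject who learns the schedule knows the device. This also stands, and it means that masking and balanced assignment belong together. Balance alone would not remove expectation in a subject who can see the device.

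A third reply is that masking may not be practicable. A reader might infer from the goggles and the matched applicator windows that subjects could be masked at almost no cost. The documents do not establish this. The goggles are protective and are also worn by the staff who operate the devices. The LED uses a belt, the laser's handling is not described, and the subject has to complete the first VAS between the two treatments. Low cost is a reasonable expectation once the devices have been checked, not a finding.

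A reader might also infer that the temperature comparison is compromised, because a verbal report of intolerable pain ends a session. That chain is possible, but nothing in the documents shows it operating, and temperature itself is read by thermocouple.

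**Conclusion.** The point holds in a limited form. Subjects are unmasked, pain is self-reported once per device, and safety is to be compared between devices, so expectation can enter the pain contrast. Its size and direction cannot be derived from the documents. The range of about 9% to 47% for an interval excluding zero rests on the assumed SD, on a common shift of 0.5 to 1.0 cm, and on an analysis that section 10.3 does not plan.

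Two stronger conclusions are not supported: that expectation is the main obstacle to attributing a pain difference to the devices, and that masking alone would remove the obstacle. The fixed side and order confound the contrast whether or not subjects are masked. The change is worth making before enrolment if a between-device pain statement is wanted. It does not call the primary endpoint into question.

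**What to change.** - **Conceal the device.** In section 7.3.2 and the consent wording, say that one device is used on each flank and that the side is not disclosed until both VAS forms are complete. Screen the applicators and consoles from the subject with a drape or occlusive eyewear, including while the first VAS is filled in. Occlusive eyewear must still give the eye protection that section 7.3.1 requires.
- **Balance the assignment.** Assign side and order at random, or balanced 5/5. Two sequences suffice: left flank first throughout, with the laser there in five subjects and the LED there in the other five. The schedule then no longer reveals the device.
- **Label accurately.** Change the Protocol Summary and sections 4.1 and 10.3 to subject-masked, operator unmasked, only if a check of both devices shows that they can be concealed.
- **Guess question.** Add it only once assignment is balanced, and report it descriptively.
- **If masking is impracticable.** State in section 10.3 that VAS is reported descriptively per device and supports no between-device pain claim.

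The cost is protocol and consent wording, a drape or eyewear, a short assignment list and at most one extra CRF item, with no extra visits. The downside is that masking may be imperfect if the devices differ in sound or feel.

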#### 4.2.1 PRIMARY ENDPOINTS

Tissue temperature profiles compared to the reference device.

#### 4.2.2 SECONDARY ENDPOINTS

### Safety objectives

Subject's assessment of discomfort and pain as measured by a 10 cm visual analog scale (VAS).

Subjects experiencing a treatment-related adverse event (AE).

## 5 STUDY ENROLLMENT AND WITHDRAWAL

### 5.1 PARTICIPANT INCLUSION CRITERIA

1. Able to read, understand and provide written Informed Consent.
2. Healthy adult, male or female,  $\geq 18$  years of age or older with skin types 1-VI.
3. Having moderate excess bilateral fatty tissue of the flanks, suitable area for non-invasive lipolysis.
4. Able and willing to comply with the treatment/follow-up schedule and requirements.
5. Women of child-bearing potential (women who have not had a hysterectomy, bilateral oophorectomy or are not postmenopausal) are required to be using a reliable method of birth control for at least three months prior to enrolment and throughout the course of the study and have a negative urine pregnancy test at baseline.

### 5.2 PARTICIPANT EXCLUSION CRITERIA

1. Pregnant, expectation of pregnancy, postpartum or nursing (<6 months).
2. History of skin disease in the area to be treated over the last 6 months.
3. Previous surgical intervention to the treatment area.
4. History of skin cancer or pre-cancerous lesions at the treatment areas.
5. Having any electrical implant anywhere in the body, such as a pacemaker or an internal defibrillator.
6. History of immunosuppressive diseases, including AIDS and HIV infection, or use of immunosuppressive medications;
7. Uncontrolled systemic diseases such as diabetes.
8. Active infections in the treatment area.
9. History of dysplastic nevi.
10. Significant concurrent skin conditions or any inflammatory skin conditions.
11. Active herpes simplex infections (e.g. cold sores), open lacerations or abrasions in the treatment area.
12. Chronic or cutaneous viral, fungal, or bacterial diseases.
13. Use of Accutane™ (Isotretinoin) within the past six months.
14. Keloid or hypertrophic scar formation in the treatment area.
15. Tattoos in the treatment area.
16. History of auto-immune disorders.
17. Erythema abigne, when identified treatments should be discontinued.
18. History of photosensitivity disorder that can be exacerbated by laser or intense light.
19. Use of medications, herbal supplements, perfumes or cosmetics that may affect sensitivity to light.
20. History of poor wound healing in the treatment area.
21. Sunburns.
22. Unable or unlikely to refrain from artificial tanning, including the use of tanning booths, prior (at least a month) and during the course of the evaluation.
23. Prior skin treatment with laser or other devices on the same treatment area within the last six months prior to study enrollment or during the course of the study.

### 5.3 STRATEGIES FOR RECRUITMENT AND RETENTION

Up to 10 subjects will be enrolled at a single site. It is anticipated that it will take up to two months to complete the study. Subjects requesting non-invasive lipolysis of the flanks will be recruited primarily from the principal investigator's clinic. Any advertising campaigns and materials will be reviewed and approved by an institutional review board (IRB) before implementation. Due to the short duration of the study (single treatment), subject retention will not be an issue.

### 5.4 PARTICIPANT WITHDRAWAL OR TERMINATION

#### 5.4.1 REASONS FOR WITHDRAWAL OR TERMINATION

Subjects are free to withdraw from participation in the study without prejudice at any time upon request. In the event that a subject drops out of the study or is withdrawn from the study, the Exit/Termination CRF form should be completed. On the withdrawal page, the Investigator should record the date of the withdrawal, the person who initiated withdrawal and the reason for withdrawal.

Reasonable effort should be made to contact any subject lost to follow up during the course of the study in order to complete assessments and retrieve any outstanding data and study medication/supplies. The records of subjects who terminate prior to completing the study will be retained and the reason for termination will be documented.

An investigator may terminate participation in the study if:

- Any clinical adverse event (AE), laboratory abnormality, or other medical condition or situation occurs such that continued participation in the study would not be in the best interest of the subject.
- The subject meets an exclusion criterion (either newly developed or not previously recognized) that precludes further study participation.

